7.2 Serious Adverse Event (SAE)

Serious Adverse Events related to the MRI procedure including MRI contrast only are to be reported. All other treatments/imaging are standard of care and therefore events are not to be reported to BCT.

[figure not shown]
A SAE is any adverse event (experience) or reaction or any untoward medical occurrence that fulfils one of the following:

- Is fatal (results in death)
- Life threatening (Note: the term “life-threatening” in the definition of “serious” refers to an event in which the patient was at risk of death at the time of the event. It does not refer to an event which could hypothetically have caused death had it been more severe)
- Required patient hospitalisation or prolongation of existing hospitalisation (Note: “inpatient hospitalisation” refers to an unplanned, overnight hospitalisation)
- Results in persistent or significant disability/incapacity
- Is a congenital anomaly/birth defect
- Is medically significant or requires intervention to prevent one or other of the outcomes listed above

Events not considered to be serious adverse events are hospitalisations occurring under the following circumstances:

- a) Planned before entry into the clinical trial for a pre-existing condition that is unrelated to the studied indication
- b) For elective treatment of a condition unrelated to the studied indication or its treatment
- c) Emergency and/or outpatient hospitalisation not resulting in admission (unless fulfilling the criteria of serious given above)
- d) Part of the normal treatment or monitoring of the studied indication and not associated with any deterioration in condition
- e) Admission to a hospital or other institution for general care, not associated with any deterioration in condition

Figure 4 SAE reporting flowchart

Abbreviations:

DQF = Data query form prepared by BCT in order to clarify or collect more information regarding the SAE report

F/U form = Follow up to original SAE report

SAE form = Serious adverse event (SAE) report prepared by investigator

Medical and scientific judgement should be exercised in deciding whether expedited reporting is appropriate in other situations, such as important medical events that may not be immediately life threatening or result in death or hospitalisation, but may jeopardise the patient or require intervention to prevent one of the outcomes listed in the definition above. These situations should usually be considered serious.

Follow up SAE information should be faxed to BCT within 24 hours of becoming aware of any change in the event. A new SAE form must be completed, stating that this is a follow up to a previously reported SAE and providing the date of the original report. The follow up information should be reported every 15 days until resolution of the event and detail the following:

- a) whether the event has resolved or continues
- b) if and how it was treated
- c) whether the patient continued or withdrew from trial participation.

The follow up SAE form must be retained by the institution, and a copy held by BCT.

All SAEs shall be reported to the responsible HREC (and the RGO in the case of multi-centre research processes) by the local Principal Investigator at the institution where the SAE occurred. A copy of the report must also be provided to BCT (and Lead Investigator in the case of multi-centre research). Ethics acknowledgment of receipt of SAE notifications shall be filed at the local institution (and at the Lead Site in the case of multi-centre research).

SAE report summaries will be distributed to investigators biannually. In addition, they will be available on the BCT website (www.breastcancertrials.org.au).

7.3 Pregnancies

In the unlikely event that a pregnancy occurs during the trial, this must be reported by the investigator to BCT within 24 hours of learning of its occurrence. Pregnancy and pregnancy follow up should be reported on the Pregnancy Notification Form but any SAE experienced during pregnancy must be reported on the SAE form.

7.4 Procedures to be followed in the case of a medical emergency

The Principal Investigator is responsible for ensuring that procedures and expertise are available to cope with medical emergencies during the trial. Patients will be provided with a list of contacts involved in the trial at their site. A letter will be sent to each patient's GP notifying them of the patient's involvement in the trial.

8 TRIAL COORDINATION

This trial will report clinical data using the BCT Online Registration System and hard copy paper CRFs for trial data submission and SAE reporting.

Trial coordination procedures for this protocol will adhere to the ICH-GCP Guidelines and will be performed according to the ANZ1002 PROSPECT Study Coordinator Manual.

The trial is sponsored and coordinated by BCT. The trial has been endorsed by the BCT Scientific Advisory Committee.

8.1 Patient Identification

All patients screened for the trial will be entered on the online screening log and all pre-registered patients will be allocated a pre-registration number.

Each patient will be assigned a Registration Number (Patient ID) on registration to the trial. This number and the patient initials are to be entered on the CRFs.

8.2 Case Record Forms

The trial will be conducted using paper based CRF templates supplied by BCT. The CRFs are to be printed as required from the BCT website (www.breastcancertrials.org.au).

CRFs must be completed in accordance with the visit schedule and submitted by fax with supporting de-identified source data to the BCT on ([contact].

CRFs are NOT to be mailed to BCT unless this procedure is specifically authorised. CRFs and source data should be readily available for review during scheduled audit visits. Further details on form completion and data submission requirements can be found in the ANZ1002 PROSPECT Study Coordinator manual.

8.3 Data Submission Schedule.

Patients entered to the main study are required to have data submitted according to the following:

- ONLINE: Pre-registration (PR1-4), Registration (A), Preoperative MRI (PreopMRI) and Surgery Forms (S) must be submitted prior to registration.
- CRF: Baseline (B form) must be submitted within 2 weeks of registration
- CRF: Follow Up (E Forms) must be submitted within 2 weeks of each protocol defined follow up visit
- CRF: SAE forms (refer to protocol section 7.2)

See Appendix J for data submission requirements for the pre-registered patient outcomes substudy.

8.4 Site Signature and Delegation of Authority Log

The names and periods of involvement of all trial personnel, including investigators, registrars and study coordinators must be recorded on the Site Signature and Delegation

of Authority Log. The PI or a Co-investigator will determine patient eligibility, obtain informed consent, plan trial treatment, make treatment related decisions, review patients at follow up visits according to the protocol and sign CRFs, including CRF segments. Registrars may be involved in these processes under the supervision of the PI or a Co-investigator.

8.5 Source Documents

All data recorded on CRFs must be able to be source data verified. Typical source documents include the following: progress notes in medical record, radiology reports, histopathology reports, haematology and biochemistry reports. Source data to verify major data points must be faxed to BCT on request.

8.6 Study Documents and Record Retention

The investigator must maintain adequate and accurate records to enable the conduct of the study to be fully documented, including but not limited to the protocol, protocol amendments, participant informed consent forms and documentation of ethics and regulatory approvals. BCT will provide investigators with the study-specific Investigator File to ensure sites file study documentation to meet GCP Essential Document requirements. The Investigator File must be kept up to date and be readily available at all times.

Trial regulatory information (including ethics correspondence and approvals) must be retained in the Investigator File in a secure storage facility for at least fifteen (15) years after the completion of the research and until BCT directs that the materials may be destroyed or sent to BCT.

Clinical records, including CRFs, all source documentation (containing evidence of trial eligibility, history and physical findings, laboratory data, results of consultations etc) must be retained in a secure storage facility for at least fifteen years after the completion of the research.

9 PATHOLOGY TISSUE COLLECTION

9.1 Tissue Banking

9.1.1 Primary Tumour (mandatory)

Submission of a sample from the primary tumour for tissue banking within one month of registration is mandatory. One de-identified tissue block from formalin fixed paraffin embedded (FFPE) biopsies of the primary tumour is to be sent to:

ANZ1002 PROSPECT Trial

Hunter Cancer Biobank

[name]

[name]

[name] One FFPE block is preferred however if a FFPE block cannot be forwarded for tissue banking, the following must be submitted:

- a) 5 unstained four micron sections on coated slides or,
- b) 5 unstained coated slides containing FNAB specimens

Specimens will be registered and tracked with the patient ID and local laboratory FFPE block number. If the banked specimen is required at any time for diagnostic purposes, it will be returned to the institution upon receipt of a written request.

All primary tumour tissue samples will be stored at the BCT Tissue Bank for use in future research projects to investigate various aspects of cancer. All future research on stored tissue will have ethics approval and will be conducted under the supervision of the BCT Scientific Advisory Committee. Research conducted on the tissue samples will not be used for commercial gain.

9.1.2 Ipsilateral Recurrence (mandatory)

All ipsilateral recurrences (invasive tumour and/or DCIS) which are proven by protocol definition (refer to 10.3.1) will be excised and a sample of the tissue must be provided to BCT for central pathology review. Samples must be forwarded to BCT within 1 month of the surgical procedure.

The following items are required:

Histopathology reports from the local recurrence

AND

1x FFPE block AND 2x unstained four micron sections on coated slides

OR if FFPE block is not available

7x unstained four micron sections on coated slides

Send to:

ANZ1002 PROSPECT Trial

Hunter Cancer Biobank

[name]

[name]

[name]

All reports, slides and blocks must be marked with the Patient ID number. Please ensure the blocks and slides are carefully packaged to avoid damage during transport.

The FFPE block from each ipsilateral recurrence will be catalogued and maintained in BCT Tissue Bank. The blocks will be available for prospective and retrospective studies approved by the BCT Scientific Advisory Committee and Human Research Ethics Committees.

The unstained slides (x2) from each local recurrence will be forwarded by BCT to the nominated central pathologist for review.

Central pathology review will include histopathological parameters (tumour type and grade, presence of DCIS and lymphovascular invasion), hormone receptors (oestrogen and progesterone receptors), and HER2 status. Testing for genes which may be inherited is not part of the central pathology review of this study.

If the banked specimen is required at any time for diagnostic purposes, it will be returned to the institution upon receipt of a written request.

10 STUDY MONITORING, AUDITING AND INSPECTING

10.1 Auditing and Inspecting

During the course of the study, BCT personnel, or any third party entitled by BCT, may conduct site audits. The investigator will provide direct access to source data/documents for trial related monitoring, audits, Human Research Ethics Committee review and any other applicable regulatory inspections.

10.2 Independent Data and Monitoring Committee (IDMC)

The BCT IDMC will review the information from interim analyses, accrual rate and local recurrence rate on an ongoing basis (every six months). The IDMC will provide recommendations to the Steering Committee, who will have responsibility for any final decisions about protocol stopping or modification.

11 STATISTICAL CONSIDERATIONS

11.1 Study design and hypothesis

The PROSPECT trial is a phase II single arm clinical trial using magnetic resonance imaging (MRI) to select patients with early breast cancer for omission of radiotherapy. The hypothesis is that MRI in association with clinical and pathological features will allow identification of truly localized early breast cancer, for which omission of RT after wide excision is appropriate.

11.2 Study endpoints and Data Analyses

11.2.1 Analysis of the primary endpoint

The primary analysis will include all registered patients.

Primary endpoint:

- Ipsilateral invasive recurrence rate (IIR) in the breast at 5 years follow up from the date of definitive excisional surgery.

It is considered that a IIRR of 5% at 5 years would be acceptable, while a IIRR of >7% at 5 years would mean that the hypothesis is not supported.

Based on these numbers, the objective is to estimate the IIRR in participants with low risk breast cancer who do not receive radiotherapy. An estimate of an overall IIRR of 5% would be clinically acceptable and based on 200 participants; this would have 90% chance of declaring a true recurrence rate of <7%. The expected number of participants who are HER2 positive to be recruited is 30-35. The expected number of participants who are HER2 negative to be recruited is 165-170. The sample size for this study is 200 registered participants. The main efficacy analysis is planned after the 100th registered subject has reached 5 years of follow up. Efficacy data will also be reviewed after the 100th registered subject has reached 2 years of follow up.

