11.2.3 Analysis of the Secondary Endpoints

Secondary endpoints:

1. Ipsilateral invasive recurrence rate in the breast at 10 years
2. Ipsilateral DCIS recurrence rate in the breast at 5 and 10 years
3. Regional recurrence rate at 5 and 10 years
4. Distant recurrence rate at 5 and 10 years
5. Contralateral breast cancer rate at 5 and 10 years
6. Breast-cancer specific survival rate at 5 and 10 years
7. Overall survival rate at 5 and 10 years

Analysis of ipsilateral invasive recurrence will also be performed when the 100th subject enrolled reaches 10 years of follow up from the date of definitive excisional surgery. Regional and distant recurrence rate will be analysed when the 100th subject enrolled reaches 5 years and 10 years of follow up from the date of definitive excisional surgery. Time to event outcomes (breast cancer specific and overall survival at 5 and 10 years) will be described using Kaplan Meier curves. The potential impact of baseline factors on recurrence and time to recurrence will be examined using appropriate regression methods (logistic, proportional hazards).

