11.2.5 Accrual rate

Average of 22 patients per year over 9 years.

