APPENDIX K: PROSPECT Sequencing Substudy

Table of Contents

1. Introduction.....	91
2. Objectives.....	91
3. Procedures.....	92
4. Study Parameters and Data Management.....	92
5. Outcomes and significance	92

1. Introduction

The Post-operative Radiotherapy Omission in Selected Patients with Early breast Cancer Trial (PROSPECT) clinical trial has used breast MRI in combination with pathological features, to prospectively identify women who might safely avoid radiotherapy due to a low risk of local recurrence.

The study has screened 443 patients over approximately 8 years of recruitment and allocated 201 patients to the no-radiation (“main study”) arm. After a median follow up of 60 months (range: 24-120), primary analysis of the 201 patients has revealed a 1% rate of ipsilateral local recurrence, with a total of 3 ipsilateral events observed at 4.5, 6.5 and 7.5 years. In addition, there was one regional recurrence and one regional/distant recurrence. The latter recurrence exhibited a different tumour morphology (lobular phenotype) compared to the index cancer (which had a ductal phenotype). There have been a similar number of contralateral events. For the subset of screened patients who were excluded from the main study (and therefore received radiotherapy), so far there have been 3 ipsilateral events in approximately 230 patients.

These findings – a similar ipsilateral and the contralateral event rate, late local recurrence, and discordant morphology between the distant recurrence and the index lesion – suggest that some of these recurrences could represent independent tumours, rather than true tumour recurrences. This is an important distinction, as adjuvant therapy given at the time of initial treatment is less likely to be effective in reducing the incidence of independent new events.

We propose to conduct sequencing of the index and subsequent lesions to determine whether they are true recurrences or whether they are independent lesions.

We also propose to analyse the index lesion where there has been a subsequent event using the PAM50 assay, to determine whether it may identify those at high risk of recurrence.

2. Objectives

Objective 1.1: Next Generation Sequencing of primary and recurrent tumours to determine whether ipsilateral local or regional and distant events are true recurrences or independent of the primary tumour

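### The 90% figure in section 11.2.1 needs 200 complete 5-year outcomes, but the main analysis is timed to 100; at that time the figure is about 87%

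*Protocol*

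**What the plan says.** Protocol section 11.2.1 defines the primary endpoint as the IIRR at 5 years from definitive surgery. It sets two benchmarks. The favourable one reads: "It is considered that a IIRR of 5% at 5 years would be acceptable". The unfavourable one is that "a IIRR of >7% at 5 years would mean that the hypothesis is not supported". The section then attaches a 90% chance of declaring the rate below 7% to an estimate of 5% and 200 participants, and adds: "The sample size for this study is 200 registered participants".

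On population and timing, the same section says "The primary analysis will include all registered patients" and "The main efficacy analysis is planned after the 100th registered subject has reached 5 years of follow up". Appendix J repeats the 100th-patient trigger. Section 11.2.5 gives the accrual: "Average of 22 patients per year over 9 years".

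Section 11.2.1 names no estimator for the IIRR. Section 11.2.3 says "Time to event outcomes (breast cancer specific and overall survival at 5 and 10 years) will be described using Kaplan Meier curves", and also names logistic and proportional hazards regression for recurrence and time to recurrence by baseline factors. It schedules a further IIRR analysis when the 100th subject reaches 10 years.

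**The concern.** The sizing statement and the analysis time stand a few sentences apart and do not match. The first treats the endpoint as a proportion of 200 patients who all have a 5-year outcome. The second fixes the main analysis at a moment when only 100 patients are sure to have one. The other patients enter with partial follow-up, so the stated precision belongs to a data set that will not yet exist.

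Two things are at stake. The first is how firmly a 5% estimate can be said to exclude the rate above 7% that the protocol calls unsupportive. The second is how the partial follow-up is handled. If events were simply divided by all registered patients, the rate would read low, in the direction that favours omitting radiotherapy.

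**Working it through.** **Inputs.** From 11.2.1: n = 200, estimate 5%, bound 7%, stated chance 90%, trigger at the 100th patient's 5 years, all registered patients included. From 11.2.5: 22 patients a year. From Appendix K: about 8 years of recruitment, 201 patients, follow-up 24 to 120 months with median 60. Confidence level, sidedness and dropout are not stated. One-sided 90% confidence and no dropout are assumed because they reproduce the stated figure.

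**1. Reproduce the stated 90%.** SE = sqrt(0.05 × 0.95 / 200) = 1.541%. Chance = Φ(0.02 / 0.01541) = Φ(1.298) = 90.3%. The matching one-sided 90% upper limit is 5% + 1.2816 × 1.541% = 6.98%. Exactly 90% needs 0.0475 × (1.2816 / 0.02)² = 195.03, so 196 complete outcomes, which leaves a slack of 4 patients. Other readings do not give 90%: taking the SE at 7% gives 86.6%, and the exact binomial P(X ≤ 13 of 200) at 5% is 87.0%.

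**2. Follow-up at the trigger.** The 100th patient enters at 100/22 = 4.55 years, so the trigger falls at 9.55 years. The 200th enters at 200/22 = 9.09 years and has about 0.45 year of follow-up. Thus 100 patients have at least 5 years, and the other 100 are spread between about 0.45 and 5 years.

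**3. Effective sample size of a censoring-aware 5-year estimate.** With constant hazard and a rare event, a Greenwood-type variance gives n_eff = 200 / [(1/5) ∫₀⁵ dt/G(t)], where G(t) is the share with follow-up of at least t. If G is 1 up to a minimum follow-up a and then falls linearly to 0.5 at 5 years, the integral is a + 2(5 − a) ln 2.

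- Planned accrual, a = 0.45: 0.45 + 9.10 × 0.693 = 6.76; divided by 5, 1.352; n_eff ≈ 148 (147 to 148 when counted patient by patient).
- Even recruitment over 8 years, a = 1.0: 1 + 8 × 0.693 = 6.55; n_eff ≈ 153.
- Minimum follow-up of 24 months, a = 2: 2 + 6 × 0.693 = 6.16; n_eff ≈ 162.

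**4. Precision at an estimate of 5%**, with the formulas of step 1:

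| Basis | Effective n | Chance of <7% | One-sided 90% upper limit |
|---|---|---|---|
| 200 complete outcomes | 200 | 90.3% | 6.98% |
| All patients, 22 a year | 148 | about 87% | 7.30% |
| All patients, 8-year recruitment | 153 | about 87% | 7.26% |
| All patients, minimum 24 months | 162 | about 88% | 7.19% |
| 100 completers only | 100 | 82.1% | 7.79% |

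**5. What a crude events/200 would show, if it were used.** The expected crude rate is the average over patients of 1 − exp(−λ min(C, 5)), with C the follow-up time and λ = −ln(1 − p)/5.

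- Planned accrual: a true 5% reads as 3.86-3.90% (22-23% low), and a true 7% as about 5.4-5.5%.
- 8-year recruitment: a true 5% reads as 4.00% (20% low), and a true 7% as 5.6%.
- Minimum 24 months: a true 5% reads as 4.26% (15% low). For a true 7%, λ = 0.014514; completers show 7%, and the rest, uniform on 2 to 5 years, show 1 − (0.97139 − 0.93000)/0.043542 = 4.94%. The mean is 5.97%.

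**6. Appendix K.** It states that "primary analysis of the 201 patients has revealed a 1% rate of ipsilateral local recurrence, with a total of 3 ipsilateral events observed". The event times it gives are 4.5, 6.5 and 7.5 years, so one event falls within 5 years. Crude figures are 1/201 = 0.5% within 5 years and 3/201 = 1.5% overall. If 100 patients entered in 5 years and 101 in the next 3 (an assumption), about 116 were at risk at 4.5 years and the Kaplan-Meier estimate is 1/116 = 0.9%. The completers give 1/100 = 1%.

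**The case against.** A reader might infer that the primary result itself will be biased by some 23%. The documents do not support that. No section prescribes events divided by 200, and the estimator may be fixed in a statistical analysis plan that is not shown, so its absence from the protocol is not in itself an error. Censored-data methods are not confined to survival either: 11.2.3 names proportional hazards for time to recurrence, and 11.3 collects recurrence dates to analyse the primary endpoint. The 1% in Appendix K also differs from the 0.5% that a crude 5-year rate would give. It fits a censoring-aware 5-year estimate or a completers-only rate. The appendix leaves the basis unlabelled, but that is terse wording and not evidence of a wrong analysis. With a censoring-aware estimate, the early trigger costs precision and adds no bias.

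A reader might also infer that the early trigger alone carries the upper limit past 7%. That limit is a reconstruction; the protocol states only a chance. It also rests on the normal approximation: the exact one-sided 90% limit for 10 events in 200 is already 7.6%. The change in the limit is informative, but the crossing of 7% is not specific to the timing.

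Finally, this is a phase II estimation study with a randomised trial proposed to follow, and a loss from 90% to 87-88% is modest. The 10-year analysis would, on planned accrual, already have 5-year data on everyone. All of this stands and limits the size of the point. It does not remove the mismatch: the stated 90% needs at least 196 complete outcomes and the trigger guarantees 100.

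**Conclusion.** The point holds as a misstatement of precision. The 90% in 11.2.1 is correct for 200 complete 5-year outcomes and is not delivered at the analysis to which the protocol ties it. There the chance is about 87% on the planned accrual, about 88% on the follow-up reported in Appendix K, and 82% if only the 100 completers are used. The implied one-sided 90% upper limit at 5% moves from 6.98% to about 7.2-7.3%, or 7.8% with completers only.

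These figures assume uniform entry, constant hazard, no dropout and the reconstructed one-sided normal calculation. A crude-rate bias of about 15-23% is a conditional risk: the protocol does not rule it out, but does not prescribe the method that would cause it. Recurrences concentrated late in the 5 years would make that bias larger.

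**What to change.** In section 11.2.1:

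1. Restate the precision for the planned analysis time: about 87% with an effective sample size of about 148 at the 100th-patient trigger, with the assumptions given. Keep the confidence level that the current statement implies. Moving to a one-sided 95% limit would change the decision rule, since that limit is 5% + 1.645 × 1.541% = 7.53% even with 200 complete outcomes.
2. State that the 5-year IIRR is a censoring-aware estimate (Kaplan-Meier or cumulative incidence) over all registered patients, so that a crude proportion is ruled out.
3. State that the 5-year IIRR will be re-estimated once all patients have 5 years of follow-up, at the latest at the 10-year analysis already scheduled in 11.2.3. On planned accrual that analysis falls at 4.55 + 10 = 14.55 years, when the last patient has 14.55 − 9.09 ≈ 5.5 years.

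The cost is a slightly less favourable stated figure and one extra estimate on data already collected.
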